7.2 Handling of missing data and outliers

For a given subject and a given efficacy/immunogenicity measurement, missing measurements will not be replaced. Therefore, an analysis will exclude subjects with missing values.

For the analysis of solicited symptoms, systemic reactions and respiratory illness symptoms, missing or non-evaluable measurements will not be replaced. Therefore the analysis of the solicited symptoms based on the Safety cohort will include only subjects/doses with documented safety data (i.e. eDiary).

7.3 Data presentation description

The following decimal description will be used for the demography, efficacy, reactogenicity and immunogenicity analyses.

Category	Parameters	Number of decimal digits
Demographic characteristics	Mean, Median	1 (One more decimal place than the raw data)
	SD	2 (Two more decimal place than the raw data)
	Min, Max	0 (Same number of decimal places as the raw data)
	% of count	1
Efficacy	VE & 95% CI	1
Humoral and Cellular Immunogenicity evaluation	GMTs including LL & UL of 95% CI	1
	GMFR including LL & UL of 95% CI	2
	SC & SP rate including LL & UL of 95% CI	1
	CMI mean, median	1
	CMI SD,	2
	P-Value	3 (0.xxx format)
Safety	% of count	1

--	--	--

For some parameters (% of count, 95% CI and VE), careful consideration may be required in some instances (e.g. very low-incidence) and in such situations, details will be described in footnotes or programming notes.

7.4 Group description

The following groups will be used for the statistical analyses.

Group order in tables	Group label in tables	Group definition for footnote
1	30 µg VLP vaccine	Subjects who have received one dose of 30 µg/strain of Quadrivalent VLP Influenza Vaccine
2	Placebo	Subjects who have received one dose of placebo.

7.4.1 Missing data analysis methods

Not applicable.

7.4.2 Handling of missing or incomplete dates

7.4.2.1 Missing or Partial AE Start Date

If only Day of AE start date is missing:

If the AE start year and month are the same as that for the first vaccination dose date, then:

- If the full (or partial) AE end date is NOT before the first dose date or AE end date is missing, then impute the AE start day as the day of first dose date; otherwise, impute the AE start day as 1.
- Otherwise, impute the AE start day as 1.

Compare the imputed AE start date with TE period to determine whether the AE is medical history or TEAE.

If Day and Month of AE start date are missing:

If AE start year = first dose year, then:

- If the full (or partial) AE end date is NOT before the first dose date or AE end date is missing, then impute the AE start Month and Day as the Month and Day of first dose date; otherwise, impute the AE start Month as January and the Day as 1.

Compare the imputed AE start date with TE period to determine whether the AE is medical history or TEAE.

If Year of AE start date is missing:

If the year of AE start is missing or AE start date is completely missing then query site with no imputation. Also compare the full (or partial) AE end date to the first dose date. If the AE end date is before the first dose date then the AE should be considered as a medical history. Otherwise, the AE will be considered as TEAE.

7.4.2.2 Missing AE Severity or Relationship

There is no imputation in cases where severity or relationship information is missing for AEs.

7.4.2.3 Missing or Partial Concomitant Medication Start/Stop Dates

Missing or partial concomitant medication start date:

- If only DAY is missing and the day , use the first day of the month.
- If DAY and Month are both missing, use the first day of the year.

Missing or partial concomitant medication stop date:

- If only DAY is missing, use the last day of the month.
- If DAY and Month are both missing, use the last day of the year.
- If DAY, Month and year are all missing, assign ‘continuing’ status to stop date

8 STATISTICAL METHODS

8.1 General statistical conventions

All statistical procedures will be completed using (SAS[®]) version 9.3 or higher.

Unless otherwise stated, all statistical testing will be two-sided and will be performed using a significance (alpha) level of 0.05. Two-sided 95% confidence intervals (CI) will be provided when relevant.

Continuous variables will be summarized using descriptive statistics, including number of subjects (n), mean, median, standard deviation (SD), minimum and maximum.

For categorical variables, summaries will include counts of subjects and percentages. Percentages will be rounded to one decimal place.

For summary purposes, baseline will be defined as the last nonmissing value on or before vaccination. All summaries will be presented by treatment group and age group, unless otherwise specified.

All subject data, including those derived, will be presented in individual subject data listings. All listings will be sorted by investigational site, subject number, date/time and visit. The vaccine group (VLP and Placebo) as well as subject's age stratum will be stated on each listing.

8.2 Subject disposition

All subjects who provide informed consent will be accounted for in this study. Subject disposition information will be summarized by treatment group and overall. Screened subjects will be presented for the overall population. The frequencies and percentages of subjects who are vaccinated in each analysis set, completed through day 21, completed the study and early study withdrawals along with primary reasons for withdrawal will be presented. The same information will be repeated for the immunogenicity subset.

The number of subjects vaccinated will be used as the denominator for the percentage calculation.

Subject disposition will be listed.

In addition, a listing will be provided to include population sets, completion of the study and withdrawal information by subject and age stratum.

Screen failures will also be listed with reason for not being randomized.

8.3 Protocol deviations

The protocol deviations by category will be summarized by treatment group and overall.

Population membership details will be listed, including reason for exclusion from each population (on randomized patients).

A listing will include the protocol deviation identified based on data recorded on the eCRF and/or protocol deviation logs from CCI (on randomized patients) and presented along with the date the deviation occurred relative to study day, deviation category and the classification of major/minor.

8.4 Demographics and baseline characteristics

8.4.1 Demographics

Age, height, weight and BMI at baseline will be summarized descriptively. Age category (18-49 years and 50-64 years), sex, race, ethnicity and influenza immunization history will be summarized using the SAS, PP and IPP.

The same information will be listed by subject and age stratum.

8.4.2 Baseline and disease characteristics

Continuous baseline variables such as OT (°C), systolic BP (mmHg), diastolic BP (mmHg), and HR (breaths/min) will be summarised by descriptive statistics in the same way as continuous demographic variables for the SAS, PP and IPP.

8.4.3 Medical history

The frequencies and percentages of subjects with medical history findings will be presented by system organ class (SOC) using the Medical Dictionary for Regulatory Affairs® (MedDRA) Version 18.1 or higher by treatment group and overall. Medical history data will be tabulated for the SAS following the order mentioned in Appendix A section 11.

The details of medical history findings will be listed by subject and age stratum.

In addition, another listing will be added to include details of influenza immunization history by subject and age stratum

8.4.4 Prior and concomitant medications

Medications used in this study will be coded by using the latest available version of the WHO Drug Dictionary.

Prior medications are medications used only before the first study vaccination (medication end date < first study vaccination date).

Concomitant medications: are defined as those medications with a start date on or after the vaccination dose of study drug or the medications started before the dose and continued during the vaccination period.

Prior medications and concomitant medications will be summarized descriptively using frequency tables by Anatomical Therapeutic Chemical (ATC) class and preferred term (or ATC Level 3) by treatment group. Details for imputing missing or partial start and/or stop dates of medication are

described in Section 7.4.2.

In addition, prior medications and concomitant medications will be listed with ATC classification and preferred term (or ATC Level 3) by subject and age stratum.

8.5 Extent of exposure

Since the subjects will receive only one dose of study vaccination, duration will not be calculated.

An individual listing will be provided to include details of vaccine administration by subject and age stratum.

8.5.1 Treatment duration

Since the subjects will receive only one dose of study vaccination, duration will not be calculated.

8.5.2 Treatment compliance

Treatment compliance is expected to be 100%, since the study treatments will be administered IM at each Investigator site by site staff. In addition, the Investigator or designated study center personnel will maintain a log of all study treatments dispensed and returned during the study.

Compliance information will not be summarized.

8.6 Efficacy analyses

8.6.1 Analysis methods

The first analysis of efficacy will be based on the occurrence of the primary endpoint (i.e., first episodes of protocol-defined respiratory illness due to laboratory-confirmed influenza) from Day 14 until the end of the surveillance period (passive and active surveillance).

Following randomization and vaccination, subjects will be instructed to report respiratory symptoms and symptoms meeting the definition of ILI from Day 14 until the end of the surveillance period (passive surveillance). The subjects will be given a reminder aid listing the symptoms of respiratory illness and ILI and contact information for the study site. During this same period, an active surveillance will also be performed via regular phone calls and occurrence of respiratory illness symptoms will be solicited a minimum of three times per week. At least one of these contacts each week will be through a scripted telephone call, with the remaining contacts via text messaging; a higher proportion of telephone contacts may be used if deemed appropriate by the clinical site (e.g. difficulty in obtaining responses via text messaging).

A respiratory illness will be defined as the occurrence of a new onset of one or more of the following symptoms that persist(s) for or reoccur(s) after a period of at least 12 hours:

- Sneezing;
- Stuffy or runny nose (nasal congestion);
- Sore throat;

- Cough;
- Sputum production;
- Wheezing;
- Difficulty breathing.

An episode is considered to extend from the first day of the first symptom to the last day of the last symptom. In most instances a new episode can only begin after resolution of all symptoms of the previous episode, with a separation of a seven-day symptom-free interval between episodes.

Within 36 hours (preferably within 24 hours) after the reporting of a respiratory illness, the clinic site will collect nasopharyngeal (NP) swabs from the subject (two per subject per event). The swabs must be collected prior to the use of any influenza antiviral treatment medication (e.g. oseltamivir, zanamivir, rapivab). If the respiratory illness starts prior to Day 14, swabs are not to be collected, even if symptoms persist beyond Day 14. One swab will be submitted for analysis by multiplex reverse transcription polymerase chain reaction (RT-PCR). In the event of a positive RT-PCR result (positive for A or B strains), the second swab will be used to attempt to isolate the virus or for additional cell-culture testing (typing, subtyping, and strain identification and genetic sequencing using HI assay against a panel of known standard ferret reference antisera to different viral strains) to determine if the virus detected is matched or similar to any of the strains covered in the vaccine formulation for the respective season.

A positive RT-PCR result will be considered a laboratory-confirmed case of influenza illness. Any respiratory illness must be followed up for 30 days following the start date; this follow up will be conducted via the planned active surveillance contacts (telephone and text messaging), using a phone script. At the end of the 30-day follow up, a questionnaire regarding disease burden due to the respiratory illness will be completed; subjects will be provided with a memory aid for use over the 30 days, to facilitate accurate reporting at the end of the follow-up period.

ILI will also be monitored during this study. A subject will be considered to have protocol-defined ILI if the following two conditions are both met between Day 14 and the end of the surveillance period:

- He/she has at least one of the following pre-defined respiratory symptoms:
 - Sore throat;
 - Cough;
 - Sputum production;
 - Wheezing; or
 - Difficulty breathing;

AND

- He/she has at least one of the following systemic symptoms:

- Fever (defined as a temperature $> 37.2^{\circ}\text{C}$ or $> 99.0^{\circ}\text{F}$);
- Chills;
- Tiredness;
- Headache; or
- Myalgia.

8.6.1.1 Treatment by center interaction analysis (multi-center study)

There is no center-interaction analysis, as randomization will be done using center as stratification factor.

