3.2 Randomization and blinding

3.2.1 Randomization

Randomization will be used to minimize bias in the assignment of subjects to treatment groups, to increase the likelihood that known and unknown subject attributes (e.g. demographic and baseline characteristics) are evenly balanced across treatment groups and age strata, and to enhance the validity of statistical comparisons across treatment groups.

Approximately 10,000 subjects are planned for randomization in a 1:1 ratio to receive the Quadrivalent VLP Influenza Vaccine at a dose of 30 µg/strain or the placebo. Randomization will be stratified by site and two age groups (18 to 49 years of age and 50 to 64 years of age in a 1:1 ratio).

Individuals will be randomly assigned to a vaccine group by use of an interactive randomization system.

Potential study subjects will be screened and assigned a subject number. Once all screening procedures, including Day 0 pre-randomization procedures, have been completed and the study eligibility is confirmed by the Investigator, the randomization numbers will be allocated to subjects within the appropriate treatment group by the randomization system.

The randomization number and treatment will be recorded along with the six-digit number for each subject in the investigational product accountability log. The Investigator will not be provided with randomization codes, but it will be possible to unblind the treatment in an emergency situation.

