5 SAMPLE SIZE AND POWER

The sample size of approximately 10,000 subjects (5,000 subjects per treatment group) was selected based on the assumption that the Quadrivalent VLP Influenza Vaccine would have a VE of at least 70% and that the attack rate in unvaccinated subjects (ARU) would be 2% or greater for laboratory-confirmed influenza cases caused by vaccine-matched strains. The sample size was chosen to have 90% power to determine whether the lower bound (LB) of the two-sided 95% CI for the primary endpoint would be greater than 40%, assuming a 10% attrition rate.

If the ARU is lower than 2%, but greater than or equal to 1.5%, this sample size will have an 80% power to determine whether the LB of the two-sided 95% CI for the primary endpoint (VE) would be greater than 40%, assuming a 10% attrition rate.

A protocol amendment will be issued to address changes to the enrollment plan or to the study extension into another season to enrol more subjects in the event of insufficient ARU.

Table 3 shows the sample size simulations result. The simulation was repeated 1000 times in order to calculate the power.

Table 3 Sample Size Simulation Result

Placebo Control AR (ARU)	VE (vs placebo)	LB of 95% CI	Power	Sample Size per Group
2%	70%	40%	90%	4430
1.50%	70%	40%	80%	4490

[Note] Under the assumptions of 70% vaccine efficacy (VE) and 2% influenza attack rate (Placebo), we expect a total of 116 to 130 cases of influenza (89 cases for Placebo and 27 cases for VLP in case of 4430 per group considering 10% dropout rate, 100 cases for Placebo and 30 cases for 5000 per group).

If the influenza attack rate is lower than 2%, but greater than or equal to 1.5%, we expect a minimum of 89 total cases.

Immunogenicity Subset

A sample size of 300 subjects (for the VLP vaccine group) was selected to ensure that the LBs of the 95% CI for the co-primary endpoints (SC and SP rates) for each strain meet CBER's criteria with 80% power (individual power is 97.4%).

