6.3 Per-Protocol (PP) set

The PP set will consist of the subjects who participated in the study until at least the end of the peak period (approximately the end of February for Europe and North America) or for at least five months or until the end of the surveillance period (other countries); had no major protocol deviations related to subject eligibility, the ability to develop a valid immune response, prohibited medication use, or the efficacy analyses; and who received the vaccine or placebo.

Subjects who received the wrong treatment, but for whom the treatment received can be unequivocally confirmed, will be analyzed as treated, provided they have no other deviations that compromise their data.

The PP set will be the primary analysis population for the efficacy and immunogenicity endpoints. The analysis of efficacy and immunogenicity analysis will be repeated using the FAS as the sensitivity analysis.

Note:

Protocol deviations and the definition of the peak influenza period will be reviewed and documented during a blinded data review prior to database lock and confirmed at the time of database lock. Since peak influenza period in each region can vary from year to year, the exact period for individual regions will be defined at the end of the season, based on reported positive influenza tests (regional surveillance reporting). The handling of missing data and whether the potential impact of any protocol deviations require the exclusion of a subject from analyses will also be considered during the blinded data review

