8.6.2.2 Methodology for computing CI

8.6.2.2.1 Exact 95% CIs

The 95% CI around RR will be calculated based on score confidence limits.

SAS® Code:^{Reference (4,5)}

```
Proc freq data= ADZ (with the appropriate analysis dataset) ;
table group*resp/relrisk (cl=SCORE) ;
run ;
```

Note: LB=1-95% Upper Confidence Limit

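### Randomisation is stratified by site and age, but the primary VE is a crude relative risk, the reason for omitting the centre interaction is invalid, and no efficacy analysis looks at region.

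*SAP*

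**What the plan says.** - **Allocation.** SAP 3.2.1: "Randomization will be stratified by site and two age groups". Protocol 6.1 agrees.
- **Primary estimate.** SAP 8.6.2 defines VE as (1 - ARV/ARU) x 100%, with success if the lower 95% limit exceeds 40%. The code in SAP 8.6.2.2.1 is "table group*resp/relrisk (cl=SCORE"). It contains no stratum variable, Mantel-Haenszel option or model. Secondary and exploratory VE use the same formula (SAP 8.6.3, 8.6.4).
- **Analysis set.** SAP 6.3: "The PP set will be the primary analysis population for the efficacy and immunogenicity endpoints". The analysis is repeated on the FAS with the same crude formula.
- **Centre.** SAP 8.6.1.1: "There is no center-interaction analysis, as randomization will be done using center as stratification factor".
- **Subgroups.** SAP 8.9.1 lists age group, matched strain, sex, race and ethnicity. Site, country and region do not appear there or in any other efficacy analysis.
- **Regional differences built into the design.** North America and Europe vaccinate in August and September, Asia in about early November (protocol Synopsis; SAP 3.1). The PP participation rule differs between Europe/North America and other countries, and regional peak periods are fixed after the season (SAP 6.3). Enrolment may extend into another season (SAP 5).

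**The concern.** Two separate things look wrong.

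First, the analysis does not reflect the randomisation. In a set formed by exclusions after randomisation, such as the PP set, balance within strata is no longer guaranteed. A crude ratio can then mix regional attack rates with differences in retention between arms.

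Second, the reason given for omitting the centre interaction confuses balance with homogeneity. Balance within centres protects the overall comparison. It says nothing about whether the vaccine works equally well in each place.

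At stake is mainly interpretation. With staggered entry and possibly different circulating viruses, a reader of a multi-country efficacy trial will ask whether the overall VE holds in each region, and the plan has no display that answers this.

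**Working it through.** **1. The plan's own figure.** Inputs from SAP 5 and 8.1: two-sided alpha 0.05; VE 70% (RR 0.30); success if the upper limit of RR is below 0.60; 4430 per group at ARU 2% and 4490 per group at ARU 1.5%. Stated power is 90% and 80%.

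Normal approximation on log RR: SE = sqrt[(1-p1)/(n p1) + (1-p0)/(n p0)] and power = Phi(ln(0.60/0.30)/SE - 1.96).
- ARU 2%: p0 = 0.02, p1 = 0.006, SE = 0.220, power 88.3%.
- ARU 1.5%: p0 = 0.015, p1 = 0.0045, SE = 0.253, power 78.3%.

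Enumeration of the two binomials gives 90.25% and 80.56% with an exact conditional limit, and 92.4% and 82.9% with the score limit that the SAP names. The stated power is reproduced, and the sample size is not in question.

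**2. Does stratifying change the primary result?** The documents give no site count and no between-site spread. The simulation assumes 25, 75 or 150 equal sites, a coefficient of variation of site attack rates of 0, 0.5 or 1.0, an age attack-rate ratio of 1.5, about 5,000 per arm and 10% random loss. It compares the crude score analysis with a Mantel-Haenszel RR over site x age.

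| Quantity | Crude | Mantel-Haenszel |
|---|---|---|
| Power, VE 70%, ARU 2% | 91.6-93.6% | 91.4-93.5% |
| One-sided error, true VE 40%, 75 sites | 2.2-2.5% | 2.2-2.4% |

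Within a scenario, power differs by at most 0.3 points and mean VE by at most 0.0001. At VE 70%, the two estimates differ by less than 0.3 to 0.9 VE points in 95% of trials.

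**3. What if PP retention differs by arm?** Assume three equal regions with ARU 0.5%, 2% and 4%, true VE 40% in each, 5,000 randomised per arm and 90% retention unless stated.

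Worked case, with vaccine retention 85% in the high-attack region:
- ARV = 0.6 x (0.5x90 + 2x90 + 4x85)/(90+90+85) = 0.6 x 565/265 = 1.279%.
- ARU = 6.5/3 = 2.167%.
- RR = 0.590, so VE = 41.0%.
- Expected events are 56.5 and 97.5, so SE = 0.166. One-sided error = Phi(-1.96 - ln(0.590/0.6)/0.166) = 3.1%.

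| Extra loss | Crude VE, 5 / 10 points | One-sided error |
|---|---|---|
| Vaccine arm, high-attack region | 41.0% / 42.0% | 3.1% / 3.9% |
| Placebo arm, high-attack region | 39.0% / 38.0% | 2.0% / 1.5% |
| Vaccine arm, low-attack region | 39.1% / 38.2% | 2.0% / 1.6% |
| Vaccine arm, all regions alike (5 points) | 40.0% | 2.5% |

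The Mantel-Haenszel estimate is 40% in every row, because the assumed loss is unrelated to outcome within a region.

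**4. Does stratified randomisation remove or reveal heterogeneity?** Assume three equal regions, exact 1:1 balance in each, ARU 2% everywhere and 4500 per arm. Overall VE is then the mean of the regional VEs, for example (90 + 90 + 30)/3 = 70%.

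| True VE by region | Overall VE | Chance of primary success | Interaction test rejects |
|---|---|---|---|
| 70 / 70 / 70% | 70% | 92.9% | 4.0% |
| 80 / 80 / 50% | 70% | 93.0% | 53.8% |
| 85 / 85 / 40% | 70% | 92.7% | 86.5% |
| 90 / 90 / 30% | 70% | 92.7% | 98.5% |

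The test sets the two like regions against the third. It assumes that the odd region is known, so a general three-region test would reject less often.

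**5. Could it be done by site?** SAP 5 expects 116 to 130 cases. That is 4.6 to 5.2 per site at 25 sites, 1.5 to 1.7 at 75 and 0.8 to 0.9 at 150. A site-level interaction test would be uninformative.

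**The case against.** The strongest reply is that nothing happens to the primary result. Power, mean VE and type I error are practically the same with or without strata. The protocol pre-specifies VE as 1 - ARV/ARU, and SAP 9 declares no change from it. Cases per site are too few for a centre test, so leaving it out is defensible. Age is not neglected: SAP 8.6.2 and 8.9.1 give VE by age group. VE by strain is also planned, and the FAS repeat is a check on PP exclusions. The loss patterns that inflate error need excess vaccine-arm loss concentrated in a high-attack region, and the documents give no reason to expect that in a single-dose, observer-blind trial with blinded deviation review.

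Most of this stands, and it rules out the stronger readings that a reader might infer: that the crude analysis biases VE, loses power or inflates type I error, or that it must be replaced as primary. The documents support none of these. The inflated cases in step 3 rest wholly on assumed retention gaps, and other patterns are neutral or conservative.

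Two things survive. A site-level test is rightly omitted, but not for the reason that the SAP gives. And VE by strain or age does not show whether VE differs by region. The FAS repeat, being crude and pooled, does not show it either.

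**Conclusion.** The point holds as a gap in the plan rather than an error in the primary result. The primary VE does not use the randomisation strata, the rationale in SAP 8.6.1.1 is a non sequitur, and region is absent from every efficacy analysis although timing and the PP rule differ by region.

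The size is as follows.
- **Primary result:** at most 0.3 points of power under the assumed site patterns, with no inflation of type I error under non-differential loss. The shift is 1 to 2 VE points, in either direction, only if retention differs by 5 to 10 points between arms within regions of unequal attack rate.
- **Interpretation:** larger. A region with VE as low as 30% could lie behind an overall VE of 70% and a 93% chance of success without any planned table showing it.

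The site counts, regional attack rates, regional VEs and retention gaps are assumptions. Stratification corrects imbalance between strata only. It does not correct exclusions that are related to outcome within a stratum, so it is no answer to that problem with a per-protocol primary set.

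**What to change.** 1. **SAP 8.6.2:** pre-specify a Mantel-Haenszel (or stratified score) VE with 95% CI by age group x region, where region is a pooling of sites, and by season if enrolment is extended. Run it on both PP and FAS. Set a rule for collapsing sparse strata and apply it blinded. Make this at least a named sensitivity analysis; the crude score interval may remain primary, as in the protocol.
2. **SAP 8.6.1.1:** replace the stated reason with the valid one, that expected events per site are too few for a site-level interaction test.
3. **SAP 8.9.1:** add VE with 95% CI by country or region, and an exploratory treatment-by-region heterogeneity test.

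The cost is SAP wording, a few program lines and the collapsing of sparse strata. It needs no new data and no change to the sample size. The wording should be settled before unblinding.
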